The NIR-TLT delivery is expected to last no longer than 7.15 minutes (429 seconds) in total (simultaneous application to the left and right forehead). The subject will be allowed to rest for 5 minutes after NIR-TLT delivery. The skin at the application sites will be inspected again after laser application. A log will be kept with the dates of delivery of the NIR-TLT.

Near Infrared Transcranial Laser Therapy in Subjects with Major Depressive Disorder: A study of Dosing with Laser.

treatment per study subject. The use of cell phones, tablets, computers or electronic devices will not be allowed during laser administration.

[figure not shown]
During treatment visits and prior to NIR-TLT, study personnel will collect tolerability (safety) and efficacy data:

1. Safety data: SAFTEE-SI (self-assessed), C-SSRS, adverse events and concomitant medication form.
2. Efficacy data - HAMD-17.

In addition to the evaluation described above, during visits 1, 9 and 18:

Prior to the NIR-TLT study, the staff will collect primary efficacy data from metric measurements and brain electrophysiology data:

1. Efficiency data:
 - a. Doctor-administered scales (1): HAMD-17, QIDS-C and CGI-S.
 - b. Patient-Reported Scales (1): ASQ and SDQ
2. Brain Electrophysiology Data - Study personnel will conduct a first 10-minute EEG recording session, treat the patient according to their NIR-TLT group randomization, and then conduct a second 10-minute EEG recording session as soon as possible after the end of treatment, but within 15 minutes.

3. Exploratory PET scan data: A PET scan will be performed on the participants selected to be part of the research subgroup, before the first treatment visit and within 24 hours of the end of the last intervention (visit 18).

4.9.3 Follow-up visit (Post Treatments) - Week 8

Near Infrared Transcranial Laser Therapy in Subjects with Major Depressive Disorder: A study of Dosing with Laser.

The next visit will occur two weeks after the last cerebral blood flow impact visit.

Purpose: The purpose of the follow-up visit is to evaluate the long-term antidepressant effect of NIR-TLT.

Procedures: During the follow-up study, staff will collect tolerability (safety) and efficacy data:

1. Safety data: SAFTEE-SI (self-assessed), adverse events and concomitant medication form.

2. Efficiency data:

- a. Doctor-administered scales (1): HAMD-17, QIDS-C and CGI.
- b. Patient-reported scales (1): SDQ and ASQ.

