 - The doctor completes this instrument based on his or her assessment of the patient's depressive symptoms, using a structured interview and defined anchor items. The goal of the HAM-D is to quantify the degree of depression in patients who already have a diagnosis of major depression. Questions focus on neurovegetative and other depressive symptoms experienced in the past 7 days. There are several different versions of the HAM-D; they differ only in the number of questions included. The standard form generally used in research studies is the 17-item Hamilton D (HAM-D-17). Responses to the questions are scored on a scale of 0-4 or 0-2, with higher scores indicating more severe pathology. Scores on the HAM-D-17 generally fall into the following ranges: a) not depressed = 0-7; b) mildly depressed = 8-13; c) moderately depressed = 14-18; d) severely depressed = 19-22; e) very severely depressed = 23 or more. Validated in Spanish by Ramos-Brieva (1986).
- **Quick Inventory of Depressive Symptomatology: Clinician-Rated Scale (QIDS-C)** - This is a brief (16-item) clinician-rated inventory of core depressive symptoms such as sleep, depressed mood, appetite, concentration, suicidal ideation, interest, energy, psychomotor retardation, or agitation. Validated in Spanish by Planas et al. (2014).
- **Clinical Global Impressions: Severity and Improvement (CGI-S, CGI-I)** - The clinician scores these two instruments from 1 to 7 based on the assessment of the subject's overall clinical status. Measured based on history and scores on other instruments: (a) depressive severity (CGI-S) and (b) clinical improvement (CGI-I). Validated in Spanish by García-Portilla (2011).
- **Anxiety Symptom Questionnaire (ASQ)** - This is a 17-item self-report questionnaire, used in Spanish, that measures the frequency and intensity of 17 anxiety symptoms, including nervousness, worry, irritability, trouble relaxing, insomnia, lack of energy, difficulty concentrating, somatic symptoms, and impaired functioning due to anxiety.

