- **Symptoms of Depression Questionnaire (SDQ)** - This is a comprehensive measure of depression that includes assessment of symptoms on the anxiety-depression spectrum. It assesses irritability, anger outbursts, and anxiety symptoms along with symptoms commonly considered to be symptoms of depression. Factor structure analysis of the SDQ identified 5 subscales, including one on the anxiety-depression spectrum, with adequate internal consistency and concurrent validity in Spanish (Pedrelli et al., 2014).
- **Columbia Suicide Severity Rating Scale (C-SSRS)** For suicidal ideation and behavior: an FDA-endorsed instrument for clinical trials. This instrument systematically tracks suicidal ideation and behavior (e.g., suicide attempts, desire to die, suicidal thoughts, plan and intent) (Posner et al. 2007) Validated in Spanish by Al-Halabí et al.(2016).
- **Adverse Event Form**- The adverse event form captures any adverse events (serious or otherwise) specifically related to the application of TLT. This form will help determine if the side effects of TLT are too great for a participant to continue in the study.
- **Concomitant Medication Form** - This form will be completed at each TLT study visit, including the screening visit, as a safety monitoring tool.

Transcranial Near Infrared Laser Therapy in Subjects with Major Depressive Disorder: A Laser Dosing Study.

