4.13 Training

Study-trained doctors who are unaware of treatment randomization will administer diagnostic assessments and rating scales. All raters will be experienced doctors who will have received criteria-specific training in the use of the study measures. Any new evaluators will receive training. Periodically, all study doctors will evaluate an audiotape during a staff meeting. These duplicate evaluations will be used both for calculating kappa coefficients and for monitoring. Differences between raters will be discussed during monitoring to identify reasons for disagreement and improve inter-rater reliability. These procedures will help us ensure that study doctors refine their diagnostic skills and will also establish common guidelines for continued use in diagnostic decision making. Inter-rater agreement will be assessed by evaluating recordings of diagnostic interviews. Kappa coefficients will be calculated every 12 months. If reliability falls below criteria ($ICC \geq 0.8$ for QIDS-C), study doctors will be retrained.

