4.17.2 Safety Monitoring

Study subjects will undergo frequent clinical assessments including depressive scores, concomitant medications, adverse events, and serious adverse events and unexpected device events will be recorded from study entry to completion. In addition, clinicians should monitor the safety of subjects by frequently asking them about their comfort during treatment delivery.

If skin erythema occurs, treatment will be discontinued. Patients will be instructed to contact the principal investigator of the study site or a member of his or her staff at any time between visits regarding adverse events or worsening of symptoms. If at any study visit, the subjects' clinical status significantly worsens from baseline (operationalized as the clinical global impression severity score, CGI-S, of 6 or greater) or if a subject develops active suicidal intent and/or plan, based on the C-SSRS scale and/or the clinical interview, the subject will be referred to the treating doctor to start an antidepressant medication or make appropriate changes in the treatment regimen. If the subject were considered to be in imminent danger as a result of suicidality, he/she would be discontinued from the study and referred to appropriate clinical treatment (see 4.9 Termination).

The two site principal investigators ([name], PI) will have bi-weekly conference calls (which will include all study staff); during these conference calls, they will discuss all adverse event reports to identify any safety concerns, based on such concerns, they may decide to temporarily discontinue study enrollment, modifications to the study protocol or terminate the study.

In addition, a Data and Safety Monitoring Board (DSMB), composed of at least 3 members not directly involved in the study, will review the SAEs annually. The research assistants responsible for data collection and storage will be aware of and comply with all regulatory requirements related to adverse events. In the event that a patient becomes ill or injured as a direct result of study participation, medical care will be provided. All adverse events (and device events) will be tracked to resolution and reported to the MGH or NKI IRB as serious in the event that:

Transcranial Near Infrared Laser Therapy in Subjects with Major Depressive Disorder: A Laser Dosing Study.

1. Not anticipated and possibly study-related (same report as SAE) or

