4.20 Summary of Risks and Benefits

4.20.1 Potential Adverse Events

Risks to the subject may include, but are not limited to, the following:

The EXPi device emits light with a wavelength longer than the human eye can see. Personnel will be trained in basic safety procedures related to the use of the device. Personnel administering the NIR-TLT will be careful not to operate the EXPi device unless it is in direct contact with the subject's skin. Both the subject receiving the NIR-TLT and the study doctor present in the NIR-TLT room will wear eye protection in the form of goggles or pads. The goggles provided with the EXPi device are in direct contact with the area surrounding the subject's eye. Since they are reusable, they should not be shared between subjects. The eye pads are disposable and should be discarded after use. The eye pads have an adhesive to adhere to the subject's eyelids, so there is a possibility of an allergic reaction.

EXPi device failure resulting in cessation of investigational therapy may cause:

1. No adverse events to our knowledge
2. Unforeseeable adverse events

Delivery of infrared energy to an inappropriate site, such as directly over the open eye, is not recommended and could pose a risk to the subject.

The application of the EXPi device may cause a slight thermal sensation of heat during use. The skin temperature is well below the thermal damage level.

Based on human clinical trial experience to date, each adverse event listed below has been reported with TLT:

1. Erythema at the application site
2. Pain at the application site
3. Discomfort at the application site
4. Heat at the application site
5. Reaction at the application site
6. Headache

Additional potential side effects of NIR-TLT, documented in previous trials, include:

- See bright colors, abnormal taste
- Feeling "out-of-body" experiences
- Insomnia, restless sleep, erratic sleep, early morning awakening.
- Vivid dreams
- Irritability
- Difficulty finding words
- Abdominal distention

Other potential risks are described below:

Transcranial Near Infrared Laser Therapy in Subjects with Major Depressive Disorder: A Laser Dosing Study.

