5.1 General Considerations

It is expected that multiple sites, randomized, sham-controlled, double-blinded, double-blinded trials will include 112 patients, randomized into four groups. Each group will receive a different dose of NIR-TLT. Group tasks and dosing will be blinded to doctors, patients and outcome assessors. Device operators will be aware of the group assignments.

The purpose of this study is to compare the antidepressant effect of four different doses of NIR-TLT and to correlate this effect with the effects of the individual dose on brain electrophysiology and mitochondrial function.

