

77. Zivin, J. A., Albers, G. W., Bornstein, N., Chippendale, T., Dahlof, B., Devlin, T., ... & Kasner, S. (2009). Effectiveness and safety of transcranial laser therapy for acute ischemic stroke. *Stroke*, 40(4), 1359-1364.3.

8. Table of Assessments

STUDY WEEK	Week 0	Week 1	Week 1 to 3	Week 3	Week 4 to 6	Week 6	Week 8
VISIT PROCEDURE	V0 Selection	V1	V2 to 8	V9	V10 to 17	V18	V19 Follow-up
Consent	■						
M.I.N.I.	■						
PET scan in study subgroup	▲					▲	
Concomitant Medication	■	■	■	■	■	■	■
Physical Examination / Lab	■ / ▲						■
Progress Note		■	■	■	■	■	■
Vital Signs	■	■	■	■	■	■	■
Adverse Events Form		■	■	■	■	■	■
ASQ	● / ▲	● / ▲	● / ▲	● / ▲	● / ▲	● / ▲	● / ▲
CGI	■	■		■		■	■
C-SSRS	■	■	■	■		■	■
HAMD-17	■	■		■		■	■
QIDS-C	■	■		■		■	■
SAFTEE-SI	● / ▲	● / ▲	● / ▲	● / ▲	● / ▲	● / ▲	● / ▲
SDQ	● / ▲	● / ▲	● / ▲	● / ▲	● / ▲	● / ▲	● / ▲
EEG		■		■		■	
Treatment- tx		▲	▲	▲	▲	▲	

Legend

- DOCTOR
- ▲ RESEARCH ASSOCIATE
- PATIENT

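### HAM-D-17 raters are not kept apart from adverse-event information, which may hint at active versus sham treatment

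*Protocol*

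**What the plan says.** **Rater blinding.** Section 4.13: "Study-trained doctors who are unaware of treatment randomization will administer diagnostic assessments and rating scales". Section 4.11 also says that outcome assessors are blinded.

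**Who rates and who records.** Section 4.10 says of the HAM-D-17: "The doctor completes this instrument based on his or her assessment of the patient's depressive symptoms". In the Table of Assessments (Section 8), the HAMD-17 row and the "Adverse Events Form" row carry the same square marker. It is read as the doctor's by elimination: the triangle is the research associate, and the circle stands on the patient self-report rows. The adverse-event row is marked at every visit from V1 to V19.

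**What the form holds.** Section 4.10: "The adverse event form captures any adverse events (serious or otherwise) specifically related to the application of TLT". Section 4.17.3 adds a grading of each event's relation to the device.

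**Same visits.** Section 4.9.2: "During treatment visits and prior to NIR-TLT, study personnel will collect tolerability (safety) and efficacy data".

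**Calls.** Section 4.17.2 says that the site principal investigators "will have bi-weekly conference calls (which will include all study staff); during these conference calls, they will discuss all adverse event reports".

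**Site reactions.** Section 4.20.1: "Based on human clinical trial experience to date, each adverse event listed below has been reported with TLT". The list includes erythema, pain, discomfort, heat and reaction at the application site. Section 3.2 gives 350 mW/cm² for each of the three active modes and 0 mW/cm² for sham.

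**Operators.** Section 5.1: "Device operators will be aware of the group assignments". The study summary agrees. Section 3.2 says that the operator is blinded.

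**The concern.** The primary outcome is a clinician's judgement, so its credibility against sham depends on the rater having no clue to treatment. The protocol states that raters are blinded but describes no arrangement that keeps them from the adverse-event record. It gives the role that rates depression a form about effects of the laser, and it brings all staff together to go through every such report.

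If site reactions are more frequent under laser than under sham, this information is a clue. A rater who suspects active treatment may score improvement more generously, which would move the active-sham differences in favour of the laser. Bias of this kind cannot be removed in the analysis.

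**Working it through.** The protocol gives no figure on this point, so the main check sets the statements side by side.

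1. *Is the rater role exposed?* Yes, as written. The doctor role has both forms (Section 8). The calls in Section 4.17.2 cover all staff and all reports. A participant who is withdrawn has the HAM-D-17 and the adverse event form at the same exit visit (Section 4.19.1). Section 4.20.1 also mentions a study doctor in the treatment room.
2. *Is the information a clue?* It may be. The active modes deliver energy and the sham delivers none, and Section 4.20.1 says that the device can cause a slight sensation of heat. Section 4.4.2 says that no dose produces a perceptible difference from sham and names skin heating as its example. The two sections disagree.
3. *What can it reveal?* Only active versus sham. The three active modes share 350 mW/cm², 429 seconds and 3.6 kJ (Section 3.2) and differ only in wave format.
4. *Does anything close the route?* No. Sections 4.11 and 4.13 state the aim of blinding but set no separation from safety data, calls or operators.
5. *Are the surrounding statements consistent?* No. Besides the conflict in step 2, operator status differs (summary and Section 5.1 against Section 3.2), and so does call attendance. Section 6.4.1 describes a bi-weekly call between the site and a sponsor monitor that includes research associates.

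**Illustration of size; every input on recognition and rating shift is assumed.** If a share pA of active and pS of sham participants are taken to be on active treatment, and each such rating shifts by k points, the active-sham difference moves by (pA − pS) × k.

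- With pA = 0.2, pS = 0, k = 2: 0.2 × 2 = 0.4 points, and 0.4 / 6.4 = 6%.
- With pA = 0.4, pS = 0, k = 3: 0.4 × 3 = 1.2 points, and 1.2 / 6.4 = 19%.

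Here 6.4 is the difference planned in Section 5.3. Any sham participant misread as active (pS above 0) reduces the shift.

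To show what an average shift b would do, assume no true effect, one active arm against sham, and a two-sided 0.05 test (Section 5.3 does not state sidedness). The SD is 7.091 and the arm size is 28, or about 22 after the planned 20% loss (28 × 0.8 = 22.4). Then SE = 7.091 × √(2/n), which is 2.14 for n = 22 and 1.90 for n = 28. The chance of a false result favouring active is Φ(b/SE − 1.96).

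| Assumed b (points) | n = 22 per arm | n = 28 per arm |
|---|---|---|
| 0 | 2.5% | 2.5% |
| 0.5 | 4.2% | 4.5% |
| 1 | 6.8% | 7.6% |
| 2 | 15.3% | 18.3% |
| 3 | 28.9% | 35.3% |

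**The case against.** Several stronger readings are tempting, and the protocol does not support them.

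- *Site reactions reveal the arm.* They cannot separate the active arms, so the comparison of pulsed with continuous wave in Hypothesis 1 is not touched by this route.
- *Sham cannot produce such reactions.* The protocol does not say so. Section 4.9.2 makes no exception for sham from the alcohol wipe, secured cap and goggles, which could cause redness or discomfort. Section 4.3 reports no significant difference in adverse-effect rates between laser at 700 mW/cm² and sham in 1410 stroke subjects, although that concerned a single session. It also reports more mild side effects under active treatment in a 16-session trial, but the most frequent were not site reactions.
- *The same person rates and records.* The table assigns a role, not an individual. The gap is that nothing requires different people.
- *Raters sit on calls with unblinded operators.* Operator status and call attendance are each described in two ways.
- *Safety questions come before the HAM-D-17.* Section 4.9.2 has a numbered list, which does not fix the order of administration.
- *The bias is 6% to 19% of the planned effect.* Those percentages follow only from assumed inputs.

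Two further points weaken the case. Under Section 4.17.2 erythema ends treatment, so that cue mainly concerns participants who are off the laser. Form order and call agendas could also be left to a site manual. Against this, Section 4.17.2 does not leave the matter open: it puts all staff on calls about all events. A difference in the frequency of reactions would also be enough to inform a rater, even if sham participants have some.

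**Conclusion.** The point holds in a limited form. The protocol claims blinded raters but gives their role the adverse-event form, brings all staff into discussion of every report, and provides no separation. Site reactions may therefore indicate active versus sham and could bias the active-sham contrasts.

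This rests on two assumptions: that site reactions are more frequent under laser than under sham, and that at least some raters see the adverse-event information of participants they rate. The protocol makes both plausible and establishes neither. The size of any bias cannot be estimated from it, and the figures above show only what assumed shifts would do. This is an inexpensive improvement worth making, not evidence that the primary comparison will be biased.

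**What to change.** 1. At V1, V9, V18 and V19, complete the HAM-D-17, QIDS-C and CGI-S before the rater sees any safety form or skin finding from that visit.
2. Order alone does not help with events known from earlier visits. Where site staffing allows, have a blinded research associate collect the Adverse Events Form, and have the principal investigator or a doctor who does not rate that participant grade causality. Do not give the form to a device operator who knows the assignment, because Section 5.5 compares adverse events between doses and that comparison would then be open to bias.
3. Amend Section 4.17.2 so that raters do not attend the adverse-event part of the calls and do not open adverse-event pages for participants they rate.
4. Reconcile Section 4.4.2 with Section 4.20.1 (perceptible heat), Section 3.2 with the summary and Section 5.1 (operator blinding), and Section 4.17.2 with Section 6.4.1 (call attendance).

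The cost is some rota planning, with no added visits. The protocol does not state how many doctors each site has, so item 2 may not be possible everywhere; items 1 and 3 need little. None of this alters safety reporting. It also does not stop a participant who feels heat from guessing the treatment and colouring the interview.

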4.17.3 Reporting Procedures for all Adverse Events

After review with the subject by study site personnel, all adverse events occurring during the study, whether or not attributed to the tPBM-2.0 device or TLT procedure, observed by the investigator or reported by the subject, will be documented in the subject's source document and on the appropriate CRF pages. The following attributes should be assigned:

1. Description of the event
2. Start Date
3. Date of resolution (if applicable)
4. Severity
5. Relation to the study set-up and / or procedures
6. Intensity
7. Action(s) taken
8. Resolution

Intensity is defined as a measure of the severity of a reaction, effect or experience. Measures are described as mild, moderate or severe. However, the event itself may be of relatively minor medical importance.

Transcranial Near Infrared Laser Therapy in Subjects with Major Depressive Disorder: A Laser Dosing Study.

The intensity of adverse events is assessed as mild, moderate or severe according to the following index scale:

Mild

The adverse event is transient, does not require treatment and does not interfere with the subject's daily activity.

Moderate

The adverse event introduces a low level of inconvenience or concern for the subject and may interfere with daily activities, but is usually ameliorated by simple therapeutic measures.

Severe

The adverse event disrupts the subject's usual daily activity and requires systematic therapy or other treatment.

If the adverse event is of such intensity in the judgment of the investigator that it warrants withdrawal from the study, the subject should be withdrawn from treatment. The subject should receive appropriate care under medical supervision until the symptoms disappear.

The relationship of an adverse event to the study device or procedure will be graded as follows:

None

The adverse event is not associated with the use of the study device.

Remote

The temporal association is such that the study device is not likely to have had an association with the observed adverse event.

Possible

This causal relationship is assigned when the adverse event:

- a) Follow a reasonable time sequence of device usage, but
- b) It could have been produced by the subject's clinical condition or other methods of therapy administered to the subject.

Likely

This causal relationship is assigned when the adverse event:

- a) Follow a reasonable time sequence of device use;
- b) It decreases when treatment is suspended;
- c) It cannot be reasonably explained by the known characteristics of the subject's clinical condition.

Definitive

This causal relationship is assigned when the adverse event:

- a) Follow a reasonable time sequence of device use;
- b) Decreases when treatment is discontinued; and
- c) It is confirmed by the recurrence of the adverse event on repeated exposure.

*For purposes of immediate reporting of unanticipated adverse events, the investigator's judgment will be considered in determining that the adverse event is "more than 50% likely" related to the use of the device or treatment procedure.

Transcranial Near Infrared Laser Therapy in Subjects with Major Depressive Disorder: A Laser Dosing Study.

